### **Outcome Measures**

Primary outcome measure: The primary outcome is the Quality of Recovery-40 questionnaire (QoR-40). It was specifically designed to evaluate quality of recovery in subject after surgery with including five aspects: emotional state, physical comfort, psychological support, physical independence and pain. There are 40 items in total, each adding 1-5 points to the score. Thus, the highest possible score is 200 points; higher scores indicate better quality of recovery. The QoR-40 will be evaluated at preoperative day 1 and postoperative day 1, 3, 7, respectively.

Secondary outcome measures: a. Incidence of postoperative complications: we will assess incidence of postoperative complications when initially find by participant or accompanying family members and diagnosed through examination or scale. Any complication after surgery will be recorded and filled in the case report form. When subject send back to ward, we will require the accompanying family members to record any complaint from subject. Assessment of incidence of postoperative complications will be going on three times and occur at postoperative day 1, 3, 7, respectively. b. The length of hospital stay (LOH): The LOH = the day of patient discharge from hospital – the day of patient admit to hospital, which is calculated base on the Hospital Information System. c. Level of stress response: The Adrenocorticotropic Hormone (ACTH), Cortisol (COR) are chosen to address the level of perioperative stress response. Blood sample taken intravenously and collected at the time of 1 day before surgery (baseline) and 1st day, 3rd day after surgery, respectively. d. Level of inflammatory response: In clinic, the C Reactive Protein and Neutrophil-lymphocyte ratio are well-known to represent the level of perioperative inflammatory response [27, 28]. Blood sample taken intravenously and collected at the time of 1 day before surgery (baseline) and 1st day, 3rd day after surgery, respectively.

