### **Methods/design:**

#### **Design**

This is a single-center, double-blind, clinical, randomized controlled study. It was approved by Ethical Committee of the Affiliated Hospital of Shandong University of Traditional Chinese Medicine on 15 June 2017 (Approval No. 2017-13th-KY) and registered at the ClinicalTrials.gov (ID. NCT03249701) before recruiting participant. The trail will base on the Consolidated Standards of Reporting Trials (CONSORT 2010) guidelines, and Standards for Reporting Interventions in Controlled Trials of Acupuncture (STRICTA). As the Standard Protocol Items: Recommendations for Interventional Trials (SPIRIT) and corresponding checklist, the participants will be recruited among inpatients who will receive total knee arthroplasty under epidural anesthesia between May 1, 2018 to Oct 1, 2018 at Department of Joint Orthopedics, Affiliated Hospital of Shandong University of Traditional Chinese Medicine, attended by [name]. All potential patients will be identified from operating schedule following the inclusion and exclusion criteria as below, and an appointed researcher will go to the ward for application of selective strategy.

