### **Study subject**

The study subject is elder inpatient who will be undergoing elective total knee arthroplasty under epidural anesthesia, age from 65 to 85 years old, ASA physical status of I-III, and agree to the informed consent form. The exclusion criteria are the subject (1) refuse to participate in the study; (2) already participate in other clinical studies; (3) is not available due to severe physical status, like ASA classification of IV; (4) required emergency patient; (5) is not suitable to TEAS requirement, e.g. pace maker or metal implant; (6) has deficiency in cognition and literacy and medical history of mental disorder, deep venous thrombosis, or history of drug abuse and acupuncture. Subject should be removed if he/she: (1) switch to general anesthesia; (2) refuses to continuous TEAS administration without any excuse; (3) gets serious adverse reactions in treatment period (e.g. cardiac arrest, comatose); (4) can't accomplish the follow-up visit; (5) acupuncturist changed; (6) low compliance patient.

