### **Intervention**

Surgical day, the subject will be transferred into operation room and calms down for few minutes with a supine position lying on the surgical bed. Acupoint stimulation administered at 30 min before epidural administration and 30 min after wound closed 2/10 HZ and the intensity adjust to maximal tolerance by participant until end of treatment. The acupuncture points are selected on

the basis of WHO Standard International Acupuncture Nomenclature, and zusanli (ST36, downward 3 inches to the hollow of patellar ligament lateral, Fig.2 a), sanyinjiao (SP6, 3 inches above the top of malleolus medialis, Fig.2 b), neiguan (PC6, 2 inches to the midpoint of wrist skin crease, Fig.2 c), quchi (LI11, the lateral end of the elbow crease when elbow flex 90 degree, Fig.2 d) are located specifically as figure.2 shown. After acupoint area disinfected by 75% alcohol, a medical electrode will be placed on the acupuncture points and connecting to an electro-acupuncture stimulator (SDZ-V, Suzhou medical technology Co. Ltd., Suzhou, China).

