### **Study protocol**

All participants will fill a demographic information sheet (including age, gender, height, weight, ASA classification status, education level, income, previous anesthesia experience/complications, medical history, anxiety and depression, preoperative examination and based line functional ability). The first assessment of patient status will take place at 1 day before surgery (baseline), and repeat at 1st day, 3rd day, 7th day after surgery.

**Safety Assessment:** We will define an adverse event as an event if more than three subjects suffer a same symptom, such as local skin rash, dizziness, and low blood sugar during the treatment-evaluation period. These events will be statistically analyzed, and treatment safety is evaluated in accordance with the research protocol. If serious adverse events occur, we will report it immediately and take actions accordingly.

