### **Statistical Analysis**

1. Content of statistical analysis: a. Dropout sample: the accuracy numbers lost and dropout rate of subjects are described, and reasons for the dropout is given. b. Balance comparison: The

comparability of subjects in two groups are compared via the baseline information assessing. c. Efficacy analysis: we will treat the QoR-40 as the primary outcome to evaluate the efficacy of TEAS treatment in improving the postoperative recovery after total knee arthroplastic, a mean and deviation as the expression of primary outcome and compared between groups using one-way ANOVA (SNK method), however, before statistic performed, a test of normal distribution of data should be used to determine whether the data are suitable for analysis using the one-way ANOVA. Additional four composite outcome measures (incidence of any postoperative complication, length of hospital stay, level of stress response, level of inflammatory response) are also used as secondary outcomes to determine the efficacy of

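### Length of stay is counted from admission, so any variation in the preoperative wait, which surgical-day stimulation cannot change, adds noise to a secondary recovery outcome

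*Combined protocol and SAP*

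**What the plan says.** Outcome Measures, secondary outcome b, gives the only definition of stay in the documents: "The LOH = the day of patient discharge from hospital – the day of patient admit to hospital", "which is calculated base on the Hospital Information System". The date of surgery does not enter, and no postoperative stay is defined anywhere.

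Other sections fix what this count contains:

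- Design: "the participants will be recruited among inpatients who will receive total knee arthroplasty under epidural anesthesia", and "All potential patients will be identified from operating schedule following the inclusion and exclusion criteria as below".
- Study subject: the patient is an "elder inpatient who will be undergoing elective total knee arthroplasty under epidural anesthesia". The Study protocol section places the baseline assessment one day before the operation.
- Intervention: "Acupoint stimulation administered at 30 min before epidural administration and 30 min after wound closed". No stimulation is planned on any earlier day.
- Statistical Analysis: the primary outcome serves "to evaluate the efficacy of TEAS treatment in improving the postoperative recovery after total knee arthroplastic", and length of stay is listed with three other secondary outcomes as further evidence on efficacy.
- Methods of Statistical Analysis: quantitative variables are compared by one-way ANOVA with the SNK method. No covariate is named.

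**The concern.** The trial asks about recovery after surgery, and treatment starts on the day of surgery. The stay, as defined, is the sum of a wait before treatment and a postoperative stay. Only the second part can carry a treatment effect. For example, a patient who waits 5 days and goes home 6 days after surgery scores 11; so does one who waits 1 day and goes home 10 days after surgery. The measure cannot tell these two recoveries apart.

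What matters statistically is how much the wait varies between patients, not how long it is. A constant wait drops out of every between-group comparison. A variable wait goes into the ANOVA error term, which generally widens the confidence interval and makes a real effect on recovery time harder to detect. QoR-40, complications, stress hormones and inflammatory markers are all assessed on days counted from surgery; length of stay is the one efficacy outcome that is not.

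**Working it through.** **The plan's own figure.** The Sample Size Calculation section concerns QoR-40 only: n = (1.96 + 1.282)² × (11.1² + 13.7²) / (176.9 − 164.3)² = 10.51 × 310.90 / 158.76 = 20.58, rounded up to 21 per group. The stated 26 is 21 × 1.2 = 25.2, rounded up. Nothing here depends on how stay is counted. The plan states no mean, SD, effect or power for length of stay.

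**Group size.** The 21 comes from a two-group calculation, but three groups are randomized. The stated total of 54 over three arms is 54 / 3 = 18 per arm before dropout. Both sizes are shown below.

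**Variance of the outcome as defined.** With postoperative stay SD s, wait SD w and correlation ρ between them:

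SD(total) = √(s² + w² + 2ρsw)

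The difference in means between arms is the same on either definition in expectation, because treatment cannot change the wait and randomization balances it on average. Only the SD changes.

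**Assumptions (none from the documents).** s = 3 days; true difference 2.5 days; ρ = 0 at first; one pairwise two-sample t-test, two-sided 0.05, as a simplification of the three-group ANOVA with SNK. Relative efficiency is s² / SD(total)². The 95% CI half-width at 21 per group is 2.021 × SD(total) × √(2/21).

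| Wait SD (days) | SD(total) | Relative efficiency | CI half-width, 21 per group | Power, 21 per group | Power, 18 per group |
|---|---|---|---|---|---|
| 0 | 3.00 | 1.00 | 1.87 | 75.0% | 68.0% |
| 0.5 | 3.04 | 0.97 | 1.90 | 73.9% | 66.9% |
| 1 | 3.16 | 0.90 | 1.97 | 70.5% | 63.5% |
| 2 | 3.61 | 0.69 | 2.25 | 59.2% | 52.4% |
| 3 | 4.24 | 0.50 | 2.65 | 46.2% | 40.4% |

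**Correlation.** Same inputs, 21 per group, against 75% with no variation in wait:

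- ρ = +0.3: power 63% at wait SD 1 and 49% at wait SD 2.
- ρ = −0.3: power 79% at wait SD 1 and 73% at wait SD 2.

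Counting from admission reduces the variance only when w² + 2ρsw < 0, that is, when ρ is negative and w/s < 2|ρ|. With s = 3 and ρ = −0.3, that means a wait SD below 2 × 0.3 × 3 = 1.8 days.

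**The case against.** The strongest reply is that the loss may be negligible. Patients are elective, come from one department's operating schedule at one centre, and exclude emergencies and ASA IV. That is compatible with a fairly uniform wait, and at a wait SD of 0.5 day power moves only from 75% to 74%. The 50% loss of efficiency needs the wait to vary as much as recovery itself. Independence is also assumed, and a negative correlation with a small wait SD reverses the result. All of this stands: the definition is certain, the size of the harm is not.

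A reader might infer that a chance imbalance in waits between small arms would pass as a treatment effect, and so count it as a second harm. The documents do not support that. Under the planned randomization the difference in mean stay is unbiased. Chance imbalance in the wait is the same variance already counted in the standard error, and it does not in itself raise the error rate of the test.

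It is also fair to say that total stay is a legitimate measure of resource use, that this is one of four secondary outcomes with no power claim, and that the assumed 2.5-day effect is generous: at 21 per group a true 1.5-day difference has only 35% power even when counted from surgery. Adjusting for the wait would also deal with the noise. These points limit the weight of the concern; none gives a reason to prefer the admission-based count as the measure of postoperative recovery.

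**Conclusion.** The point holds as a mismatch between a secondary outcome's definition and the question it serves, with a likely loss of precision. It does not hold as bias, and it does not touch the QoR-40 result or the sample size derived from it.

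The size cannot be established from the documents. Under the stated assumptions with an independent wait, power ranges from 75% down to 46% at 21 per group, and from 68% down to 40% at 18 per group, as the wait SD goes from 0 to 3 days. The loss is nil if waits are equal, larger if patients who wait longer also recover more slowly, and absent or reversed if the correlation is negative and the wait SD small. To read the lower end of these ranges as what this trial will lose would go beyond the documents. The change is worth making because it is nearly free and makes the outcome measure what it is used to judge.

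**What to change.** In Outcome Measures, secondary outcome b, define the secondary efficacy outcome as postoperative length of stay: day of discharge minus day of surgery, with dates from the same Hospital Information System. Report admission-to-discharge days by group as a descriptive figure.

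The cost is one sentence. The date of surgery is already needed to time every postoperative assessment, so no new data, patients or procedures are required. The downside is that total stay is no longer the tested measure.

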### Sample Size Calculation

This trail contains two groups. A sample size estimation formula can be used to calculate the numbers of subjects in each group, base on two-groups, randomly, controlled design.

$$n = \frac{(Z_{1-\alpha} + Z_{1-\beta})^2 \cdot (\sigma_1^2 + \sigma_2^2)}{\delta^2}$$

where  $n$ ,  $\sigma$ ,  $\delta$  represent the sample size in each group, standard deviation, mean difference of two groups, respectively. In a condition of  $\alpha = 0.05$ ,  $\beta = 0.1$  with a two sided test, we obtain  $Z_{1-\alpha} = 1.96$  and  $Z_{1-\beta} = 1.282$ . According to previous data by Bai et al, the primary outcome of QoR-40

in the article is  $176.9 \pm 11.1$  vs.  $164.3 \pm 13.7$  as compare experimental group to control group ( $p = 0.006$ ), the sample size for each group was 21 cases and the final sample size estimated in each group was 26 cases with adding a 20% dropout rate. Totally 54 subjects are needed.

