#### **Participants**

All participants will be randomly assigned to experimental group (group E), placebo group (group

P) and control group (group C) at a ratio of 1:1 on the basis of digital random numbers generated by SPSS.17.0 software. For reducing the selection bias, an appointed researcher ([name]) will be responsible for randomization.

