### **Randomization**

According to the digital random numbers generated by SPSS.17.0 software, all participants will be assigned to experimental group (group E), placebo group (group P) and control group (group C) randomly and equally. For minimal risk bias of selection and others, a specific appointed researcher ([name]) will be in charge of the process of randomization. A sequence number will be allotted to an ensured qualified subject and a sealed envelope method is used to reduce allocation bias: the envelope is dark and opaque, sealed, content inside can't be seen even under bright light.

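### The sample size is worked out for two groups and totals 54, but three equal groups are randomised: 54 gives 18 per arm and less than the planned 90% power

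*Combined protocol and SAP*

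**What the plan says.** The Sample Size Calculation section opens with "This trail contains two groups" and applies a two-group formula for a difference in means, with alpha 0.05 "with a two sided test" and beta 0.1. The planning values are QoR-40 scores of 176.9 (SD 11.1) for experimental and 164.3 (SD 13.7) for control. It reports that "the sample size for each group was 21 cases", and then that "the final sample size estimated in each group was 26 cases with adding a 20% dropout rate. Totally 54 subjects are needed".

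The Randomization section states that "all participants will be assigned to experimental group (group E), placebo group (group P) and control group (group C) randomly and equally". The Participants section names the same three groups, although it gives the allocation as "at a ratio of 1:1 on the basis of digital random numbers generated by SPSS.17.0 software". The Intervention part describes each of the three arms separately.

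The Statistical Analysis section plans a one-way ANOVA with SNK comparisons for the primary outcome, yet describes the baseline comparison as one between two groups. No section gives a three-arm sample size or any total other than 54.

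**The concern.** The number of arms, the size per arm and the total contradict one another. Someone working from the total stops enrolment at 54; someone working from 26 per group in three arms stops at 78. The documents do not say which governs.

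If 54 governs, each pairwise comparison of the primary outcome rests on 18 patients per arm before any loss. That is fewer than the plan says it needs after loss. The protocol would then claim 90% power for a trial that does not have it, and a non-significant E versus C result would carry less information than the claim implies.

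A second mismatch adds to this. The formula is for a single two-group z-test, whereas the planned SNK procedure uses a stricter critical value when the two means compared are the extremes of three.

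**Working it through.** **Inputs (Sample Size Calculation section).** Difference 176.9 − 164.3 = 12.6; SDs 11.1 and 13.7; two-sided alpha 0.05 (Z = 1.96); power 90% (Z = 1.282); dropout 20%. The root-mean-square SD is √((123.21 + 187.69)/2) = 12.47.

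**Per-group figure.** n = (1.96 + 1.282)² × (11.1² + 13.7²) / 12.6² = 10.51 × 310.90 / 158.76 = 20.58, rounded up to 21. The plan's 21 reproduces.

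**Dropout step.** 21 × 1.2 = 25.2, rounded up to 26, is the plan's figure. Dividing instead, 21 / 0.8 = 26.25, rounded up to 27. With 26 randomised, 26 × 0.8 = 20.8 remain, just under 21.

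**Total.**
- Two arms: 2 × 26 = 52; 2 × 27 = 54.
- Three arms: 3 × 26 = 78; 3 × 27 = 81.
- 54 over three arms: 54 / 3 = 18 randomised per arm, and 18 × 0.8 = 14.4, so about 14 evaluable.

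The total of 54 therefore fits only a two-arm trial with 27 per arm. For three arms it is 24 to 27 patients short.

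**Power for E versus C.** The standardised difference is 12.6 / (12.47 × √(2/n)): 3.03 at n = 18, 2.67 at n = 14 and 3.27 at n = 21. The z figure is Φ(that value − 1.96), and the t figure comes from the noncentral t distribution with 2n − 2 degrees of freedom. The SNK column is a simulation (40,000 repetitions per setting). It assumes a group P SD of 12.47, which the documents do not give, and a group P mean of 164.3, 170.6 or 176.9.

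| n per arm | Plan's z formula | Two-sample t | SNK, three groups |
|---|---|---|---|
| 14 (54 randomised, 20% loss) | 76% | 73% | 61–67% |
| 18 (54 randomised, no loss) | 86% | 84% | 74–80% |
| 21 (evaluable number required by the plan) | 91% | 89% | 82–87% |

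The lowest SNK value in each row occurs when the group P mean lies midway between E and C.

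**Chance of missing the assumed effect if 54 is kept.** With no loss it is 14% (z), 16% (t) or 20–26% (SNK). After the planned 20% loss it is 24% (z), 27% (t) or 33–39% (SNK). The plan states 10%.

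**The case against.** The contradiction itself is hard to dispute, but several points limit what follows from it.

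- **The power loss is conditional.** If 26 per group governs, 78 are enrolled, about 21 per arm are evaluable and E versus C power is 89% by t-test, essentially as stated. This stands: the shortfall applies to the total of 54. On that reading, though, the printed total is wrong and still needs correcting.
- **Fourteen per arm is the unfavourable case.** It needs the full 20% loss and an analysis of completers. The Methods of Statistical Analysis section invokes intention-to-treat and then restricts efficacy to those who completed and followed the protocol, so the analysed set is not settled. This also stands, and both cases are shown for that reason. Even with no loss, power is below 90% on every calculation.
- **The dropout step is largely convention.** Multiplying by 1.2 rather than dividing by 0.8 changes the result by one patient per arm. Agreed; the point does not depend on it.
- **The SNK figures need a group P SD that is not in the documents.** Letting that SD run from 9 to 16 moves power at 14 per arm from about 53% to a little over 70%. The SNK column is therefore illustrative. The z and t columns need no assumption about group P and already show the shortfall.

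**Conclusion.** The section is wrong as written and must be corrected before its figures are relied on. A two-arm total has been attached to a trial with three equally randomised arms, and no reading makes the number of groups, 26 per group and 54 in total agree.

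If 54 is the target, E versus C power by t-test falls from the stated 90% to about 84% with no loss and about 73% after the planned loss. It is lower again under SNK. These results take the plan's effect size and SDs at face value; the 73% also assumes that the 20% loss occurs and that those patients are not analysed.

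The calculation supports E versus C only. No planning difference is given for E versus P, so that comparison has no stated power basis.

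**What to change.** Rewrite the Sample Size Calculation section for three arms, and bring the Participants, Randomization and Statistical Analysis sections into line on the number of groups, the allocation ratio and the total. Two routes are open.

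1. **Keep 54.** State 18 randomised and about 14 evaluable per arm. Restate E versus C power as about 73% by t-test after loss (84% without), and about 61–67% under SNK with the assumed group P SD disclosed. This needs only rewording and no extra patients; the price is a less favourable power statement.
2. **Keep 26 per group.** State a total of 78, or 81 with 27 per group from 21 / 0.8. This means 24 to 27 more patients than 54 (44–50% more) at a single centre with a recruitment window of May 1 to Oct 1, 2018. It restores roughly 90% for one unadjusted pairwise comparison. Under SNK, 21 evaluable per arm still gives only about 82–87%, and the text should say so.

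On either route, state that the planning effect is E versus C, that E versus P was not powered, and which set of patients the power figure refers to.

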### **Methods of Statistical Analysis**

According to the principle of intention-to-treat (ITT), our data will contain all subjects enrolled. Efficacy and safety measures will be analyzed in accordance with protocol strictly, thus, only subjects who completed the entire trial and followed the protocol requirements should be analyzed. Quantitative and qualitative variables are described statistically with  $X \pm SD$  and count numbers, separately. Quantitative variables will be analyzed by one-way ANOVA (SNK method) in statistic, a normal data distribution needed before performance. Qualitative variables will be analyzed using either  $\chi^2$  test or Fisher' s exact test. All statistical tests are two-sided, and P value  $< 0.05$  will be considered to be statistically significant. Statistical analysis will be performed using SPSS 17.0 software for application.

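### The stated 26 per group and the stated total of 54 contradict each other, for two groups (52) and for the three groups randomized (78)

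*Combined protocol and SAP*

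**What the plan says.** All the figures are in the Sample Size Calculation section of the combined protocol and SAP. It opens by fixing the number of arms: "This trail contains two groups". It gives a formula for comparing two means, with α = 0.05, β = 0.1 and a two-sided critical value of 1.96. The QoR-40 inputs come from a cited study: 176.9 ± 11.1 against 164.3 ± 13.7.

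Three results follow:

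- Before dropout: "the sample size for each group was 21 cases".
- After dropout, and in total: "the final sample size estimated in each group was 26 cases with adding a 20% dropout rate. Totally 54 subjects are needed".

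No working is shown between 21 and 26, or between 26 and 54. The Randomization section describes a different number of arms, with participants "assigned to experimental group (group E), placebo group (group P) and control group (group C) randomly and equally". The Participants section likewise names three groups with equal allocation.

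**The concern.** The per-group figure and the total stand in adjacent sentences, and no equal allocation at 26 per group produces 54. Someone recruiting to this plan cannot tell whether to stop at 52, 54, 78 or 81.

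Two things are at stake. The per-group figure is what any restated total has to be built on, so it must be settled first. The total also decides how many patients each arm receives. If recruitment stops at 54 and those patients are spread over three equal arms, each arm has 18, which is below the 21 evaluable patients the plan says it needs, even before anyone is lost.

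**Working it through.** **Inputs** (all from the Sample Size Calculation section): means 176.9 and 164.3, so δ = 12.6; SDs 11.1 and 13.7; Z values 1.96 and 1.282; dropout 20%.

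**Step 1. Reproduce the evaluable number.**

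n = (1.96 + 1.282)² × (11.1² + 13.7²) / 12.6² = 10.5106 × 310.90 / 158.76 = 20.58, rounded up to 21. The plan's 21 is confirmed.

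**Step 2. Apply the 20% dropout.** The plan does not say how it did this. The candidate routes are:

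| Route | Result | Rounded up |
|---|---|---|
| Unrounded 20.58 / 0.8 | 25.73 | 26 |
| Stated 21 / 0.8 | 26.25 | 27 |
| Stated 21 × 1.2 | 25.2 | 26 |

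The stated 26 is reproduced by the first and third routes. It would also result from rounding 26.25 to the nearest whole number.

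**Step 3. Multiply up.**

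| Per group | Two groups | Three groups |
|---|---|---|
| 26 | 52 | 78 |
| 27 | 54 | 81 |

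The stated 54 matches 27 in each of two groups. It also equals 3 × 18. It matches nothing at 26 per group.

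**Step 4. Check power at each retained number.** Inverting the plan's formula, power = Φ(12.6 × √(n / 310.90) − 1.96), where n is the evaluable number per group.

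| Situation | n | Power |
|---|---|---|
| 26 enrolled, 20% lost | 20.8 | Φ(1.299) = 90.3% |
| 27 enrolled, 20% lost | 21.6 | Φ(1.361) = 91.3% |
| 54 over three arms, none lost | 18 | Φ(1.072) = 85.8% |
| 54 over three arms, 20% lost | 14.4 | Φ(0.752) = 77.4% |

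The first two rows show that 26 and 27 both reach 90% by the plan's own method. The last two show that 18 per arm does not.

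**The case against.** The strongest reply is that this is a clerical slip of two patients (52 against 54) with no effect on planned power. For a two-group trial, that stands: both per-group figures keep the 90% target. It does not stand for the trial as randomized. With three arms, the gap between 54 and 78 or 81 is 24 or 27 patients.

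A reader might go further and infer that 26 fails the plan's own dropout allowance, because 26 × 0.8 = 20.8 is below 21. The documents do not support that. The formula requires 20.58, and 21 is only that number rounded up; 20.8 exceeds 20.58. Cutting 20.8 to 20 whole patients does give 89.2% power, but keeping 20 of 26 means losing 6, or 23.1%, which is more than the plan assumes. Losing 5 (19.2%) leaves 21 and 90.6%.

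A reader might also infer that 26 came from multiplying 21 by 1.2 and that 27 is therefore the only correct figure. That is conjecture, since dividing 20.58 by 0.8 also gives 26.

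One argument does lean towards 27. The planned analysis is ANOVA rather than a z test. With a pooled-SD t test on the same inputs, power is 88.9% at 20.8 and 90.0% at 21.6. The difference is small, however, and the plan's calculation is explicitly normal-based, so this supports choosing 27 without showing that 26 was an error.

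**Conclusion.** The contradiction between 26 per group and 54 in total holds. It needs only multiplication and depends on no convention. It amounts to 2 patients if there are two groups and 24 if there are three (78 − 54). At 27 per group the two-group total agrees with 54, but the three-group total is 81, which is 27 more than stated.

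It is not established that 26 is too few, that β = 0.1 is missed at 26, or that the dropout step used the wrong method. That 54 was built from 27 per group is plausible, but the document does not say so.

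The power figures assume the plan's means and SDs, its normal approximation, equal arms, a 20% loss in each arm, and a single pairwise comparison at two-sided 0.05 with no adjustment for having three groups.

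**What to change.** In the Sample Size Calculation section:

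1. State one per-group figure and how dropout and rounding were applied. Use 27 if the stated 21 is divided by 0.8, which agrees with 54 for two groups. Use 26 if the unrounded 20.58 is divided by 0.8, in which case the two-group total becomes 52.
2. Restate the total for the arms actually randomized, and correct the sentence that says there are two groups if there are three. For three equal arms the total is 81 (at 27) or 78 (at 26).
3. If 54 is the real total for three arms, replace the per-group figure with 18 and report the resulting power by the plan's formula: about 85.8% before dropout and about 77% after 20% dropout.

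Changing 26 to 27 and stopping there would not be enough. The section would then agree with itself, but its total would still cover only two of the three randomized arms.

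The first change costs one sentence. The second costs a corrected total and, if three arms are kept at 26 or 27 each, 24 or 27 more patients than the plan now states. The third needs no extra patients but requires the plan to acknowledge lower power.
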